5.2.3. Assigning Case Definition

The case definitions for mild, moderate, and severe/critical COVID-19 are provided in the CTP Section 8.1.2. This section provides guidance on how these will be applied.

- Information on symptoms is to be collected from the eCOA (see Appendix 6 of the CTP) and from the eCRF entered by the site (including AEs linked to COVID-19). In case the sources are inconsistent (i.e., on a single calendar Day one source records the symptom and another source does not record that same symptom) the symptom is considered to have been present on that Day.
- A sign or symptom is considered as absent or present for a COVID-19 episode: any sign or symptom is considered present if observed in the eCOA or eCRF for the COVID-19 episode, and absent if not.
- Signs or symptoms occurring at any time during the episode are used for the application of the case definitions.
- The application of the criteria is independent of duration; if a sign or symptom is present at any time, the sign or symptom is considered to be present. [Note that for a suspected COVID-19 case to be tested, at least one symptom of suspected COVID-19 has to be present for 24 hours, and not otherwise explained (Section 8.1.1. of the CTP: “New onset or worsening of any 1 of these symptoms, which lasts for at least 24 hours, not otherwise explained”). For case classification the information from the eCOA and eCRF is taken independent of duration or alternative explanations.]
- Fever will be assessed independent of method (oral, armpit, ear, or rectal).

- The definitions of *mild*, *moderate*, and *severe/critical* are mutually exclusive, where the most severe category takes priority.
- At the time of resolution of the COVID-19 episode, the collected information will be applied against the clinical case definition. For the purpose of continuous monitoring, the clinical case definition will be included as soon as analysis-ready independent of resolution (see above). In case symptoms worsen afterwards, increasing the classification of severity, the next continuous monitoring analysis will analyze the case according to the highest degree of severity at that time (see Section 5.9).

As there can be specific unforeseen situations where definitions as detailed in the SAP did not cover the specific situation, the Sponsor will at that time define additional data handling guidelines based on an assessment (blinded to treatment assignment) as close as possible to the intent of the rules as specified above. The Study Statistics and Programming team at the Sponsor will provide their additional data handling guideline to the SSG, which will be documented in the Data Presentation Specification document (DPS).

5.2.4. Symptomatic COVID-19 Case Derivation

Some symptoms lead to suspicion of a COVID-19 and are used as triggers to proceed with home-collection of the nasal swabs for SARS-CoV-2 testing as based on interaction of the participant with the site. The list of symptoms used as triggers for testing are provided in Section 8.1.1. of the CTP. A triggering symptom may lead to a (confirmed) positive SARS-CoV-2 test, where the case may fail to reach the mild case definition (or worse) at any time during the episode. These cases are not considered as symptomatic. In other words, symptomatic COVID-19 cases are those that are at least of mild severity as defined below.

For any case to be considered a case at least one sample needs to have a SARS-CoV-2 positive RT-PCR from the central laboratory (University of Washington). The derivations for mild, moderate, and severe/critical are given below.

5.2.4.1. Mild COVID-19 Case Derivation

A case will be considered of mild COVID-19 severity if one (or more) of the following symptoms is observed, if not satisfying the definition of a moderate or severe/critical disease severity [black, terminology from eCOA or blue, terminology from the eCRF]:

- Fever ($\geq 38.0^{\circ}\text{C}$ or $\geq 100.4^{\circ}\text{F}$) or Vital signs eCRF
- Sore throat / [Sore throat](#)
- Loss of appetite / [Malaise](#)
- Feeling generally unwell (run down) / [Malaise](#)
- Fatigue (tiredness) / [Malaise](#)
- Physical Weakness] / [Malaise](#)
- Headache / [Headache](#)

- Muscle aches/pains / [Myalgia](#)
- Diarrhea / [Gastrointestinal Symptoms](#)
- Vomiting / [Gastrointestinal Symptoms](#)
- Nausea / [Gastrointestinal Symptoms](#)
- Abdominal/stomach pain / [Gastrointestinal Symptoms](#)
- Cough / [Cough](#)
- Chest congestion (mucus in chest)
- Runny nose
- Wheezing
- Skin rash
- Eye irritation/discharge
- Chills
- Uncontrollable body shaking/shivering /[Shaking chills or rigors](#)
- Decreased sense of smell / [Anosmia \(olfactory or taste disorders\)](#)
- Decreased sense of taste / [Anosmia \(olfactory or taste disorders\)](#)
- Red or bruised looking feet or toes / [Chilblains/pernio \(red or bruised looking feet or toes\)](#)

5.2.4.2. Moderate COVID-19 Case Derivation

For the definition of moderate COVID-19 severity there are two separate criteria, either if met would be sufficient to be considered as moderate (if not satisfying the criteria of severe/critical disease):

1. At least one **sign** or symptom (as derived from the Medically-attended COVID-19 Form (MA-COV) form or [other CRF source or eCOA](#)):
 - Respiratory Rate \geq 20 breaths/minute [or vital signs CRF](#)
 - Abnormal saturation of oxygen (SpO2) but still $>93\%$ on room air at sea level [or vital signs CRF \(=94%\)](#)
 - Clinical or radiologic evidence of pneumonia [or AE preferred term "COVID-19 PNEUMONIA"](#)
 - Radiologic evidence of DVT
 - *Shortness of breath (difficulty breathing)*

OR

2. Two (or more) signs or symptoms from of the following (black, terminology from eCOA or [blue, terminology from the eCRF](#)):

- Highest temperature was $\geq 38.0^{\circ}\text{C}$ or $\geq 100.4^{\circ}\text{F}$ or [CRF](#)
- Heart rate ≥ 90 beats/minute or [vital signs CRF](#)
- Chills or Uncontrollable body shaking/shivering /[Shaking chills or rigors](#)
- Sore throat / [Sore throat](#)
- Cough / [Cough](#)
- At least one from [Loss of appetite, Feeling generally unwell (run down), Fatigue (tiredness), Physical Weakness] / [Malaise](#)
- Headache / [Headache](#)
- Muscle aches/pains / [Myalgia](#)
- At least one from [Diarrhea, Vomiting, Nausea, Abdominal/stomach pain] / [Gastrointestinal Symptoms](#)
- Decreased sense of smell or Decreased sense of taste / [Anosmia \(olfactory or taste disorders\)](#)
- Red or bruised looking feet or toes / [Chilblains/pernio \(red or bruised looking feet or toes\)](#)

5.2.4.3. Severe/Critical COVID-19 Case Derivation

A case will be considered severe/critical if (black, terminology from the Medically-attended COVID-19 Form (MA-COV) or [blue, terminology from the eCRF](#)):

- Clinical signs at rest indicative of severe systemic illness (respiratory rate ≥ 30 breaths/minute, heart rate ≥ 125 beats/minute, oxygen saturation (SpO_2) $\leq 93\%$ on room air at sea level, or partial pressure of oxygen/fraction of inspired oxygen ($\text{PaO}_2/\text{FiO}_2$) <300 mmHg)
- Respiratory failure (defined as needing high-flow oxygen, non-invasive ventilation, mechanical ventilation, or extracorporeal membrane oxygenation [ECMO])
- Shock (defined as systolic blood pressure <90 mmHg, diastolic blood pressure <60 mmHg, or requiring vasopressors)
- Significant acute renal or hepatic dysfunction
- Numbness, tingling, or weakness face or limbs (neurologic dysfunction)
- Difficulty speaking or forming speech (neurologic dysfunction)
- Difficulty understanding speech (neurologic dysfunction)
- Feelings of confusion (neurologic dysfunction)
- [Admission to the ICU \(Medical Encounters eCRF\)](#)
- [Death \(SAE form\)](#)

In addition, severe/critical cases can be identified through the use of the following vital signs:

- [SpO₂ ≤ 93%](#)
- [Heart rate ≥125 beats/minute](#)
- [Respiratory Rate ≥30 breaths/minute](#)

5.2.4.4. US FDA Harmonized COVID-19 Case Derivation

A case will be considered satisfying the FDA harmonized COVID-19 case criteria if at least one of the following symptoms was recorded during a COVID-19 episode (black, terminology from eCOA [or blue, terminology from the eCRF](#)):

- Fever ($\geq 38.0^{\circ}\text{C}$ or $\geq 100.4^{\circ}\text{F}$) [or CRF](#)
- Cough / [Cough](#)
- Chills (or Uncontrollable body shaking/shivering) [/Shaking chills or rigors](#)
- Sore throat / [Sore throat](#)
- Shortness of breath (difficulty breathing)
- Fatigue (tiredness) / [Malaise](#)
- Muscle aches/pains / [Myalgia](#)
- Headache / [Headache](#)
- Decreased sense of smell / [Anosmia \(olfactory or taste disorders\)](#)
- Decreased sense of taste / [Anosmia \(olfactory or taste disorders\)](#)
- Chest congestion (mucus in chest)
- Nasal congestion (stuffy nose)
- Runny nose
- Joint aches/pains
- Diarrhea / [Gastrointestinal Symptoms](#)
- Vomiting / [Gastrointestinal Symptoms](#)
- Nausea / [Gastrointestinal Symptoms](#)

The FDA harmonized COVID-19 case definition is independent of the case definition above, meaning that each subject with a case of molecularly confirmed COVID-19 is considered as an FDA harmonized case (yes/no), and considered as either a case of mild, moderate, or severe/critical case.

5.2.5. Asymptomatic or undetected Sars-COV-2 infection

5.2.5.1. Definition

If a participant does not fulfil the criteria for suspected COVID-19 based on signs and symptoms which would classify them as mild, moderate, or severe by the definitions,

AND

has a SARS-CoV-2 positive RT-PCR or molecular test result from any available respiratory tract sample (eg, nasal swab sample, sputum sample, throat swab sample, saliva sample) or other sample

OR

develops a positive serology (non-S protein) test

Then, the participant will be considered to have experienced asymptomatic or undetected COVID-19.

A molecularly confirmed positive RT-PCR for SARS-CoV-2 will need to be captured in the eCRF.

5.2.5.2. Classification

As for symptomatic COVID-19 case classification, a similar approach will be taken to identify asymptomatic infections or undetected cases via an algorithmic approach. Cases will then be reviewed and classified as being an "Asymptomatic SARS-CoV-2 infection" by the Clinical Severity Adjudication Committee.

Relevant definitions for programmed algorithm:

Identification of potential asymptomatic SARS-CoV-2 infections via PCR: in the event of a positive PCR, the cases will be reviewed for the presence of signs and/or symptoms of COVID-19 since baseline employing the definitions of onset and resolution of section 5.2.2. In the absence of signs and/or symptoms, the case will be classified per algorithm as asymptomatic.

Identification of potential asymptomatic or undetected SARS-CoV-2 infections through seroconversion:

- **SARS-CoV-2 seroconversion with onset Day >28** is based on the available data from Day 71, Month 6 and/or unblinding visit. If positive at any timepoint while the subject was seronegative at baseline (and at Day 29 for the PP analysis after day 28), a subject is considered seroconverted. If Day 29 is missing or not available, then the subject is considered negative on that Day.
- **SARS-CoV-2 seroconversion from Day 1 to Day 29**, is based on the available data on day 29. If positive at day 29 while the subject was seronegative at baseline or missing, a subject is considered seroconverted between day 1 and day 29.

- A **seroconverted participant** is a subject with serological conversion without an earlier molecularly confirmed (SARS-CoV-2 positive RT-PCR or molecular test result from any available respiratory tract sample)

Upon algorithmic identification, cases will be evaluated as being an "Asymptomatic SARS-CoV-2 infection" by the Clinical Severity Adjudication Committee as follows:

- Asymptomatic SARS-CoV-2 infections or seroconverted participants as assigned via the programmed algorithm will be reviewed for the presence of possible COVID-19 signs and symptoms since baseline up to 7 days prior to the first positive PCR or up to the day of the first positive serology test.
- If no presence of signs/symptoms, the algorithm will be accepted and no further review by the CSAC and the case classified as Asymptomatic SARS-CoV-2 infections .
- If at least one sign or symptom present, those cases will be sent to the CSAC for review for a possible undetected symptomatic COVID-19.
 - If reviewed by the CSAC as asymptomatic sars-cov-2 infections, cases will be classified as asymptomatic infections.
 - Seroconverted cases reviewed by the CSAC as symptomatic will be classified as **serologically confirmed COVID-19** and evaluated according to the accepted/reviewed severity and onset date.
 - PCR+ cases reviewed by the CSAC as symptomatic will be classified and evaluated according to the accepted/reviewed severity and onset date

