Based on epidemiological modeling for the targeted study countries, province/states of the various site locations, the annualized incidence of moderate to severe/critical COVID-19 cases meeting the primary endpoint definitions has been predicted to be 1.4% for the October-November timeframe. The estimate incorporates that real-world-evidence data and literature data only detected and reported a fraction of SARS-CoV-2 infections.

Furthermore, it includes that, based on literature and real-world-evidence data, only a fraction of all infections meets the moderate to severe/critical COVID-19 case definition and the fraction varies by age as well (increasing with higher ages). Moreover, projections for the selected study regions indicate that incidences will decline over time. Finally, seroprevalence rates are expected to vary between 5-15%.

For the purpose of sample size evaluation, an incidence assumption of moderate to severe/critical COVID-19 cases meeting the primary endpoint definition of 1.4% during the first 3 months of the

study, with a 50% reduction in Month 4, and 62% reduction in the months thereafter is assumed in combination with a seroprevalence rate of 10%.

The epidemiological situation will remain uncertain during the course of the study: actual seroprevalence rates, degree of social distancing and use of personal protective equipment during the study, local regulations (eg, potential lockdowns, other vaccines if available) potentially becoming in effect during the course of the study and potential drop-outs from the study may impact the disease incidence rate.

To that end, the maximum sample size of approximately 60,000 participants will be selected. This sample size is selected, based on the uncertainty of the epidemiological situation in combination with the ability to provide a high probability (approximately 90%) to reach a time to signal within 8 months of the study for a vaccine with an assumed 60% VE.

Based on an estimated case-hospitalization ratio of 2.5% and estimates obtained from reported real-world-evidence data of 3-10% of all SARS-CoV-2 infections meeting the severe/critical COVID-19 definition, this will provide a reasonable likelihood of observing 5 severe cases in the placebo group within the same time frame (8 months).

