Some violations will not lead to exclusion of the subject from the PP, but data from the time-point of major protocol deviation onwards will be excluded as of from that moment from the analysis (if all data after double-blind vaccination is excluded, the participant will be excluded from the PP):

- use of prohibited concomitant medications or medical conditions that were judged to probably impact the efficacy of the vaccine based on blinded medical review will be assessed on a case by case basis and documented before confirming a case for continuous monitoring or data base lock
- administration of another SARS-CoV-2 vaccine before or during the trial

The following variables are relevant for in/exclusion of analyses:

- Seropositive or seronegative at baseline. A baseline serologic test for past or current infection with SARS-CoV-2 will be performed for all participants. Samples for the baseline serologic tests will be sent to the central lab for testing. Results will be categorized as positive or negative. If a participant is seropositive at baseline, the participant will be excluded from the PP set. In case the test result is missing or unknown the participant will be considered as seronegative for analysis purposes.
- PCR positive (PCR+) or negative (PCR-) at baseline: a sample for SARS-CoV-2 infection at baseline will be collected for each participant. For participants with a positive SARS-CoV-2 infection during the study this sample will be tested. If a participant was analyzed PCR+ at baseline, the participant will be excluded from the PP set. A missing value will be considered as PCR- for analysis purposes.

Timing of the infection: the onset of a symptomatic SARS-CoV-2 infection is defined in section [5.2](#). Based on the onset of infection, subjects will be included as

- For analysis with onset after double-blind vaccination: if onset occurred on or after Day 2 in the study (i.e. the Day after double-blind vaccination or beyond). At this stage there is however no expectation that the double-blind vaccination has achieved its full efficacy.
- For analysis with onset at least 14 days after double-blind vaccination: if onset occurred at or after Day 15. Subjects with an onset prior or at Day 14 will be excluded from the analysis.
- For analysis with onset at least 28 days after double-blind vaccination: if the onset occurred on Day 29 or beyond. Subjects with an onset prior or at Day 28 will be excluded from the analysis.

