5.5.2. Key Confirmatory Secondary Endpoint(s) and Estimand(s)

5.5.2.1. Definition of Endpoint(s)

Endpoint Label	Endpoint definition
Any symptomatic infection (BOD)	
For all subjects with a symptomatic, molecularly confirmed COVID-19 episode, classification based on any severity will be included.
 
Weight-adjusted analysis for severe disease will be done as follows. Any case of mild or moderate COVID-19 will be given a score of 1, severe/critical COVID-19 cases will be given a score of 2.
 
Subjects without a symptomatic, molecularly confirmed COVID-19 episode are implicitly categorized as 0.

Asymptomatic infection	
Asymptomatic infection with an onset at least 28 days after vaccination is considered as a subject with either serologic conversion (day 71 or month 6) or with a SARS-CoV-2 positive RT-PCR or molecular test result from any available respiratory tract sample (eg, nasal swab sample, sputum sample, throat swab sample, saliva sample) or other sample but both without a previous suspected, symptomatic COVID-19 episode according to the adjudication committee (asymptomatic as defined in section 5.2.5). Additionally, both types of asymptomatic infections will be analyzed separately as well (based on PCR versus based on serology).

	
Supportive endpoints:
 
 1. Seroconverted participants will be defined as participants with a serologic conversion (day 71 or Month 6 and/or unblinding visit) and without a previous SARS-CoV-2 positive RT-PCR or molecular test result from any available respiratory tract sample (eg, nasal swab sample, sputum sample, throat swab sample, saliva sample) or other sample regardless of prior symptoms 2. Subset of asymptomatic infections based on PCR results from the Month 6 and/or unblinding visit 3. Asymptomatic infections between Day 1 and Day 29 will also be analyzed as a supportive endpoint. If positive at Day 29, while the subject was seronegative at baseline, a subject is considered seroconverted.
All infections (Any SARS-CoV-2 Infection)	First occurrence of SARS-CoV-2 infection (serologically, including serologically symptomatic confirmed, and/or molecularly confirmed ^a) with onset at least 28 days after double-blind vaccination with study vaccine.

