Severe infection	Per-Protocol analysis set Sero-Negative subjects with onset of infection at least 14 and at least 28 days post double-blind vaccination	PP, SN/SP, Day 28* FAS, SN, Day 1 FAS, SN/SP, Day 1*
Medical intervention	Per-Protocol analysis set Sero-Negative subjects with onset of infection at least 14 and at least 28 days post double-blind vaccination	PP, SN/SP, Day 28* FAS, SN, Day 1 FAS, SN/SP, Day 1*
Asymptomatic or undetected infection	Per-Protocol analysis set Sero-Negative subjects with onset at least 28 days post double-blind vaccination	FAS, SN Day 1
Asymptomatic or undetected infection from Day 1 to Day 29	FAS, SN Day 1	
PP=per-protocol, SN=sero-negative subjects, Day 1/28=including infections with onset 1 day/28 days post double-blind vaccination, SP=seropositive subjects, FAS=full analysis set		

(*Any analysis regardless of serostatus will be done only if 7 or more events observed in the group of subjects who were seropositive at baseline.

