For cases, the follow-up time is defined as the time between double-blind vaccination and the time of onset of infection (timepoint of a positive N-protein Elisa for asymptomatic subjects).

For supportive endpoints, Vaccine efficacy will be estimated with a 95% confidence intervals (as described in appendix 8).

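### The Day 1 to Day 29 seroconversion rule counts a Day 29 positive with no baseline result as a new infection, which dilutes the supportive VE for that window

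*SAP*

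**What the plan says.** Section 5.2.5.2 gives the programmed rule for conversion from Day 1 to Day 29: "If positive at day 29 while the subject was seronegative at baseline or missing, a subject is considered seroconverted". The stated exclusion is that a seroconverted participant "is a subject with serological conversion without an earlier molecularly confirmed" infection.

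The endpoint table in Section 5.5.2.1 words the same endpoint without mentioning a missing baseline: "If positive at Day 29, while the subject was seronegative at baseline, a subject is considered seroconverted". Section 4 sets the general convention for baseline serology: "In case the test result is missing or unknown the participant will be considered as seronegative for analysis purposes".

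On status, Section 5.5.2.1 says "Asymptomatic infections between Day 1 and Day 29 will also be analyzed as a supportive endpoint". Table 8 has a row for "Asymptomatic or undetected infection from Day 1 to Day 29" and assigns it to the seronegative full analysis set from Day 1. Section 5.5.4.3 gives the estimator: "For supportive endpoints, Vaccine efficacy will be estimated with a 95% confidence intervals (as described in appendix 8"). Section 1.1 also lists conversion between baseline and Day 29 among the secondary endpoints.

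Section 5.4.5 has a supportive analysis that drops participants without a baseline serology result. It is listed only for moderate to severe/critical COVID-19 with onset at least 14 and at least 28 days after vaccination.

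**The concern.** A conversion needs a negative starting value. Without one, a Day 29 positive shows only that infection happened at some time before Day 29. For PCR-confirmed symptomatic disease, treating a missing baseline as negative does little harm, because a wrong baseline serostatus does not itself create an event. For seroconversion the baseline result is half of the event definition, and the same convention turns past infection into a case.

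No stated step removes these cases. Adjudication is triggered by signs or symptoms since baseline, and without any the algorithm's classification stands. It does not ask whether infection predates enrolment. Under Section 4 the stored baseline PCR sample is tested only for participants with a positive SARS-CoV-2 infection during the study.

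At stake is the Day 1 to Day 29 VE estimate and its interval. The exploratory any-infection endpoint over the same window (Section 5.6.1.1) would inherit the rule through its serological component.

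**Working it through.** The SAP states no power, event count or expected VE for this endpoint, so there is no figure to reproduce. The check works out how far the rule moves VE under the SAP's own planning inputs.

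**Inputs from the SAP**
- About 40,000 participants at 1:1, so 20,000 per arm (Sections 3.1 and 1.2).
- Seroprevalence: the sample-size section plans "in combination with a seroprevalence rate of 10" per cent and expects 5-15%.
- Incidence of moderate to severe/critical COVID-19: 1.4% annualized at planning; 3.8% to 6.3% in the text added with Protocol Amendment 3 (Section 3.1), taken here as annualized too.
- Placebo infection mix (Section 3.5.3): 45% asymptomatic and 55% symptomatic, of which 60% + 20% = 80% moderate or severe. Moderate/severe is therefore 0.55 × 0.80 = 44% of infections, and there are 0.45/0.44 asymptomatic infections per moderate/severe one.
- VE = 1 − n2/n1 at equal follow-up (Appendix 8).

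**Assumptions**
- Missing baseline fraction m: 0.1%, 0.5% and 1%. The SAP gives none.
- Participants with a missing baseline have the same seroprevalence as the rest and a Day 29 sample, and their antibody persists to Day 29.

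**Step 1: are these positives old or new?** The 28-day risk of asymptomatic infection is incidence × 28/365 × 0.45/0.44. That is 0.11% at 1.4% incidence and 0.49% at 6.3%. Among placebo participants with a missing baseline who are positive at Day 29, the pre-enrolment share is s/[s + (1−s) × risk], with s the seroprevalence:
- s = 10%: 0.10/(0.10 + 0.9 × 0.0011) = 99%, down to 0.10/(0.10 + 0.9 × 0.0049) = 96%.
- s = 5%: 98% down to 91%.
- s = 15%: 99% down to 97%.

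**Step 2: true and false events at 10% seroprevalence**
- T = 20,000 × 0.9 × incidence × 28/365 × 0.45/0.44 = 20 (1.4%), 54 (3.8%) or 89 (6.3%) on placebo.
- F = 20,000 × 0.10 × m = 2, 10 or 20 per arm at m = 0.1%, 0.5% or 1%.

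**Step 3: effect on VE.** Randomization puts the same expected F in each arm:

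expected VE = 1 − [T(1−VE) + F]/(T + F) = VE × T/(T + F)

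For a true VE of 50%:

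| Missing baseline | F per arm | T = 20 | T = 54 | T = 89 |
|---|---|---|---|---|
| 0.1% | 2 | 45% | 48% | 49% |
| 0.5% | 10 | 33% | 42% | 45% |
| 1% | 20 | 25% | 36% | 41% |

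At 1% missing, varying seroprevalence over 5-15% as well widens the range to 19-45%.

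**Step 4: if early VE is low.** With a true VE of 10% and 1% missing, the expected reading is 5%, 7% or 8%, a shift of 2 to 5 points.

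**Step 5: conversions after Day 28.** Section 5.2.5.2 requires a negative Day 29 result for the per-protocol analysis and counts a missing Day 29 as negative. A participant with a missing baseline and a positive Day 29 result is therefore not a case there. A participant missing both results and positive at Day 71 or later can be.

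**The case against.** The strongest reply is that little depends on this endpoint. It is supportive, reported with a 95% interval, and carries no alpha. The bias runs toward zero, so it cannot create a false efficacy claim. Section 4 itself says that full efficacy is not expected for onset counted from the day after vaccination, so a true VE of 50% may be generous for this window. A baseline test is planned for everyone, so the missing fraction could be near 0.1%, where the loss at 50% is only 1 to 5 points. The estimate is also imprecise: a true VE of 30% with 14 against 20 events has an approximate 95% interval of −39% to 65%, and with 62 against 89 events about 4% to 50%. At 1% missing, 30% would read 15% or 25% in those two cases, well inside the intervals. All of this stands and limits the weight of the point. It does not make the rule right: the bias is systematic and avoidable.

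A reader might also infer that Sections 5.2.5.2 and 5.5.2.1 hold rival definitions, since only the first mentions a missing baseline. The SAP does not support that. Under Section 4 a missing result is already seronegative, so the two can be read as the same rule. The difference is one of wording.

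**Conclusion.** The concern holds for the supportive Day 1 to Day 29 endpoint. Following the SAP as written adds mostly pre-enrolment infections to both arms and multiplies the true VE by T/(T+F). The direction does not depend on the assumed figures. The size does: at 10% seroprevalence and a true VE of 50%, it runs from a loss of 1 to 5 points at 0.1% missing to a reading of 25-41% at 1% missing, and it is smaller if early VE is low. Because the SAP does not give the missing fraction, the documents do not support calling the bias large.

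A reader might go further and infer that the confirmatory asymptomatic endpoint is compromised. The documents do not support that either: it counts onset after Day 28 in the per-protocol set and is affected only when baseline and Day 29 are both missing. No calculation here puts a size on that route. The primary conclusion is untouched.

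**What to change.** 1. For seroconversion endpoints, state an exception to the Section 4 convention and require a documented negative baseline N-serology. Exclude participants with a missing baseline from both numerator and denominator of the Day 1 to Day 29 analysis. Deleting the reference to a missing baseline from Section 5.2.5.2 alone would change nothing, because Section 4 would still class these participants as seronegative.
2. Align the wording of Sections 5.2.5.2 and 5.5.2.1.
3. Report the number of missing baseline serology results by arm.
4. For conversions after Day 28, keep the definition and add a sensitivity analysis, modelled on the one in Section 5.4.5, that excludes participants missing both baseline and Day 29.

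The cost is SAP wording, one changed derivation, one extra run and a count. The downside is losing the participants without a baseline result from this one endpoint, which should be few.
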